The utility of smartphone applications for patient care is increasingly being appreciated and in Europe, clear guidelines exist for developers who aim to develop software as a medical device (6). The advantage of using smartphone applications is that little specialised equipment is needed and, if a digital support programme is proven successful, implementation can be widely performed at low cost.

In the current context of the Covid-19 pandemic, HF patients are particularly suffering from the difficulty to meet their cardiologist and HF nurse on a regular basis. Developing the possibility for remote monitoring is a key alternative to avoid re-hospitalization or severe clinical cardiovascular outcome.

We present the design of the Bedicare-HF trial, which aims to take digital support research a step further. It uses an implementation design approach in which a real-life setting will be approximated. The trial aims thus to not only demonstrate the effectiveness of a smartphone-based HF digital support approach but also the feasibility of implementation in a European healthcare context. Also, it aims to evaluate the cost-effectiveness of a smartphone-based digital support approach.

Objectives

The objectives of this study are to demonstrate feasibility, acceptability, adoption, sustainability, and safety of a smartphone-based digital support system in the healthcare system in Belgium and to demonstrate effectiveness, to evaluate the implementation cost of the system, and to demonstrate cost-effectiveness.

Methods

Study design

The study design is a multicentre implementation trial. The conduct of the study is guided by good clinical practice (GCP) in accordance with the Declaration of Helsinki and the laws and regulations applicable in Belgium. Written approval from the Ethics Committees at all involved centres is required and informed consent must be provided by each patient.

Patient recruitment

Eligible patients are consecutive patients that are hospitalised for HF decompensation. The patients will be included in the programme during their hospitalisation or up to one week after hospitalisation. All eligible patients will be offered to participate. At the time of inclusion,

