Table 2 – intervention design. ECG: electrocardiogram. ePRO: electronic patient-reported outcome. NT-proBNP: N-terminal prohormone of brain natriuretic peptide. KCCQ-12: Kansas City Cardiomyopathy Questionnaire. EQ5D: EuroQol 5-dimension questionnaire. HeartQoL: Health-related quality of life questionnaire. PHQ9: patient health questionnaire-9. HLS-EU-Q16: European Health Literacy Survey Questionnaire. EHFSB-9: European Heart Failure Self-care Behaviour scale revised into a nine-item scale. SUTAQ: Service User Technology Acceptability Questionnaire. WPAI : work productivity and impairment.

Health economic analysis

The costs considered for the cost-effectiveness analysis are direct costs of the smartphone-based digital support intervention and the care utilisation recorded during the inclusion of the trial. The costs for the digital support intervention consist of costs for data management using the application, costs for devices that are provided in selected patients (blood pressure monitor, weighing scale), and personnel costs for inclusion and time spent on follow-up of alarms.

Information on care utilisation will be collected at the end of the trial. Former studies have demonstrated that hospitalisation costs are the key driver of HF-related costs (7,8). This study will thus focus on reduction in length of hospital stay and reduction in rehospitalisations after initial hospitalisation. The 30-day and 90-day rehospitalisation rates will be assessed. All hospital-related costs will be collected from the hospital billing and financial departments. A distinction will be made between scheduled and non-scheduled hospitalisations. Scheduled hospitalisations for elective procedures and scheduled visits with the cardiologist or general practitioner will not be included in the cost-evaluation.

Implementation cost and cost-effectiveness will be assessed in this trial following a pre-post economic model. A historical cohort of all patients hospitalised for HF on a cardiology ward in 2019 in all participating centres will be assessed for comparison. Hospital bills and hospital administrative data based on the international classification of disease (ICD)-codes will be collected. Propensity matching will be applied.

QOL and healthcare-related costs will be collected in selected patients refusing to participate in the smartphone intervention.

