Cost reduction between the intervention group, the historical cohort, and the participation refusals will be calculated. Costs and outcomes (utilities) will be compared by calculation of the incremental cost-effectiveness ratio (ICER) (ICER = $(\text{cost}_{\text{intervention group}} - \text{cost}_{\text{historical cohort}}) / (\text{effectiveness}_{\text{intervention group}} - \text{effectiveness}_{\text{historical cohort}})$). The incremental cost represents the difference in total average cost per patient between the intervention group and the historical cohort or the participation refusals. Effectiveness will be calculated by comparing QOL in the intervention group versus the participation refusals.

Study endpoints

The endpoints that will be assessed are summarized in Table 3. As specified before, the objectives of the study are to demonstrate positive implementation measures (e.g. feasibility) as well as to demonstrate cost-effectiveness. Secondary objectives include assessment of clinical impact, based on measurement of clinical endpoints as specified in Table 3. Implementation outcome variables will be assessed using a mixed-method design. Patient and caregiver parameters will be calculated (e.g. time spent using the application). Questionnaires will be used to assess patient variables. Semi-structured interviews in a selection of patients and caregivers will be performed to assess further outcome variables regarding implementation.

Implementation outcome variables	
Feasibility and patient acceptability	SUTAQ, semi-structured interviews.
Caregiver acceptability and burden of care	SUTAQ, semi-structured interviews, daily time spent by case nurses using the platform
Adoption and sustainability	Number and percentage of patients refusing inclusion, of patients continuing application usage after 6 months. Total time-percentage ratio of patients using the application throughout the trial.
Implementation cost	Cost-related data: healthcare resource use, hospital days, tests, procedures, health expenditure. Cost-effectiveness: healthcare cost data, WPAI questionnaire, ICER. Cost of hospital stay at inclusion.
Quality of life, literacy and patient self-care	KCCQ-12, EQ5D, HeartQoL, PHQ9, HLS-EU-Q16, EHFSB-9, SUTAQ.
Clinical outcome measurement	
Combined endpoint	Unplanned CV readmission and all-cause mortality

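### The ICER is the only measure combining cost and effect, yet it is uninformative for the result sought (lower cost, better QOL), and its printed formula and the text use different comparators

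*Protocol*

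**What the plan says.** The Objectives section includes the aim "to evaluate the implementation cost of the system, and to demonstrate cost-effectiveness", and Study endpoints repeats that "the objectives of the study are to demonstrate positive implementation measures (e.g. feasibility) as well as to demonstrate cost-effectiveness". Under Health economic analysis, costs and utilities are to be compared through the ICER. The printed formula subtracts the historical cohort from the intervention group in both the numerator (cost) and the denominator (effectiveness). End-of-trial assessment and Table 3 also name the ICER, and no other measure combining cost and effect appears.

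The direction hoped for is clear. The cost analysis says "This study will thus focus on reduction in length of hospital stay and reduction in rehospitalisations after initial hospitalisation", and "Cost reduction between the intervention group, the historical cohort, and the participation refusals will be calculated". The Conclusion speaks of improved health outcomes.

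On comparators, the text after the formula says that "The incremental cost represents the difference in total average cost per patient between the intervention group and the historical cohort or the participation refusals", and then that "Effectiveness will be calculated by comparing QOL in the intervention group versus the participation refusals". For the 2019 historical cohort the section lists hospital bills and administrative data. For selected refusals it lists both QOL and healthcare costs.

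**The concern.** There are two linked problems, both in text that the Protocol itself fixes.

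First, a ratio of two differences is useful when both differences have the same sign and the reader knows which sign. The study looks for opposite signs: cost down, QOL up. There the ratio is negative, its size has no ordering, and the mirror result (cost up, QOL down) gives the same number.

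Second, the formula as printed needs an effectiveness value for the historical cohort, which the listed data do not supply. If the cost difference is taken against the historical cohort and the effect difference against the refusals, the quotient is not the ICER of the app against either alternative.

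The Discussion links a successful result to reimbursement in Belgium, so the combined measure is likely to be read as the headline economic result.

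**Working it through.** **Inputs.** From the Protocol: the objective, the formula, the hoped-for direction, 165 intervention patients and at least 165 refusals (Sample size). It states no expected cost or utility difference, SD, threshold or ICER value, so there is no figure to reproduce. All euro and utility values below are assumptions.

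**Step 1: algebra.** Write ΔC and ΔE for the cost and effect differences, intervention minus comparator. ICER = ΔC/ΔE, so (−a)/(+b) = (+a)/(−b) for any a and b. Incremental net monetary benefit is NMB = λ·ΔE − ΔC, where λ is the willingness to pay per unit of effect.

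| ΔC | ΔE | ICER | NMB, λ = 20,000 | NMB, λ = 40,000 |
|---|---|---|---|---|
| −1,000 | +0.02 | −50,000 | +1,400 | +1,800 |
| +1,000 | −0.02 | −50,000 | −1,400 | −1,800 |
| −2,000 | +0.04 | −50,000 | +2,800 | +3,600 |
| −1,000 | +0.04 | −25,000 | +1,800 | +2,600 |
| −100 | +0.02 | −5,000 | +500 | +900 |
| +1,000 | +0.02 | +50,000 | −600 | −200 |
| −1,000 | −0.02 | +50,000 | +600 | +200 |

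Rows 1 and 2 are opposite results with one ICER. Row 3 is twice as good as row 1 with the same ICER. Row 4 (larger gain) and row 5 (smaller saving) both move the ratio toward zero, although one is better than row 1 and the other worse. Rows 6 and 7 show that a positive ICER also needs its quadrant stated. NMB separates every pair.

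**Step 2: comparators side by side.**
- Formula: cost and effectiveness both from the historical cohort.
- Text: cost from the historical cohort or the refusals; effectiveness from the refusals.
- Data listed: historical cohort, bills and administrative data only; selected refusals, QOL and costs.

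The formula therefore cannot be computed as printed from the listed data. Replacing only its denominator as the text directs gives a mixed ratio. Only the refusals have both terms.

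**Step 3: illustration of size.** Assume a cost SD of EUR 8,000, a QALY SD of 0.12, 165 per group, and independent normal estimates. SE(ΔC) = 8,000·√(2/165) = 881. SE(ΔE) = 0.12·√(2/165) = 0.0132.

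For a saving of 500 and a gain of 0.0125:
- P(ΔC < 0) = Φ(500/881) = 0.715 and P(ΔE > 0) = Φ(0.0125/0.01321) = 0.828.
- Cheaper and better: 0.715 × 0.828 = 0.592. Costlier and worse: 0.285 × 0.172 = 0.0490.
- The ICER is negative in 0.641 of trials, and 0.0490/0.641 = 7.65% of those are costlier and worse.
- At λ = 20,000, mean NMB = 250 + 500 = 750 and its SE = √(881² + 264²) = 920. The 95% interval lies above zero with probability Φ(750/920 − 1.96) = 12.6%.

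| True saving / gain | ICER negative | Costlier-and-worse share of negatives | NMB interval above zero, λ = 20,000 / 40,000 |
|---|---|---|---|
| 500 / 0.0125 | 64.1% | 7.65% | 12.6% / 16.2% |
| 1,000 / 0.02 | 82.4% | 1.0% | 33.1% / 41.8% |
| 1,500 / 0.03 | 94.5% | 0.05% | 62.7% / 74.8% |
| 2,000 / 0.04 | 98.7% | 0.001% | 86.1% / 93.9% |

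For the first row, a correlation between cost and effect of −0.3 to +0.3 moves the 7.65% to between 11.0% and 4.2%.

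**The case against.** The strongest reply is that the section already calculates the cost reduction and compares QOL as separate results. Both signs are known before any ratio is formed, and a reader who sees a saving with a QOL gain knows that the app dominates. This stands. A reader might infer that the study could not tell a cheaper, better app from a costlier, worse one, or that its objective can be neither met nor refuted. The documents do not support that: the ambiguity lies in the ratio alone.

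It can also be said that the Protocol states no ICER threshold, no rule that a given ICER demonstrates cost-effectiveness, and no confidence interval on the ratio. That is true, so criticism of such a rule or interval would be aimed at something the plan does not contain. A threshold, a bootstrap or an acceptability curve may sit in a later plan, and their absence here is not the point. What remains is the choice of combined measure, which the Protocol does fix; a later plan that used net benefit would be replacing it.

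Finally, the numerical instability depends on the assumed effect and is mostly imprecision, which any summary shares. That also stands: net benefit removes the ambiguity, not the sampling error.

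None of these replies touches the comparator mismatch.

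**Conclusion.** The point holds on two counts. The ICER, as the sole combined measure for an objective of demonstrating cost-effectiveness, is uninformative in the case the study looks for: it is negative, does not rank results, and equals its mirror image. This is exact algebra and needs no assumption, but it applies only when cost falls and QOL rises; if both fall, the ratio is positive. Separately, the printed formula and the text disagree on the comparator for effectiveness, and the listed data cannot fill the formula as printed.

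The practical harm is moderate, because the two differences are also to be calculated and show the quadrant. The simulated shares rest wholly on assumed effects, SDs, independence and 165 per group (no matched size is given for the historical cohort). They run from 7.65% to under 0.1%, so they illustrate the issue and do not predict an error rate.

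**What to change.** Amend Health economic analysis as follows.

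- Use one comparator for both terms of any combined measure: the refusals, for whom QOL and costs are both planned. Correct the formula accordingly. Keep the propensity-matched historical cohort for a cost-only comparison.
- Report the cost difference and the effect difference, each with an interval, and state dominance by quadrant.
- Base the cost-effectiveness conclusion on incremental net monetary benefit over a willingness-to-pay range stated beforehand, with a patient-level bootstrap interval.
- Give an ICER only when both differences have the same sign, and say which quadrant it lies in.

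The cost is wording and a standard bootstrap. A willingness-to-pay range must be named. The result may be inconclusive: under the assumed SDs, the interval favours the app in about 13% to 16% of trials for a saving of EUR 500 with a gain of 0.0125, and about 86% to 94% for EUR 2,000 with 0.04.

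The refusals have limits as a comparator. They are self-selected, costs are planned only in selected refusals, and Patient recruitment asks for their QOL at 6 and 12 months without mentioning a baseline. The amended text should say how the effect difference is formed from those data.

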patients must be in New York Heart Association (NYHA) class II, III, or IV with a left ventricular ejection fraction (LVEF) of ≤40%. The inclusion and exclusion criteria are shown in Table 1. A total of 165 patients will be included over 6 month. In total, 11 hospitals (local investigators) in Belgium with an HF clinic employing at least one certified HF nurse will be participating in patient recruitment. Patients are not randomised and will all be participating in the smartphone digital support intervention.

A screening register will be kept including reasons why eligible patients that do not participate are disregarding inclusion. Patients refusing participation will also be asked to complete a quality of life (QOL)-questionnaire at 6 months and 12 months which will be answered online. A total of 165 patients (who do not want to participate) will be asked to answer this questionnaire.

So the app will be made available to 165 patients for home monitoring and another group of 165 patients without an application will be asked to answer quality of life questionnaires.

Patients who agree to use the application can continue to use it after the study, if they wish.

Inclusion criteria	Exclusion criteria
Diagnosed with HF – NYHA class II-IV	Acute coronary syndrome
LVEF ≤40%.	High urgent listed for heart transplantation
Hospitalisation due to decompensated HF at the moment of inclusion or up to 1 week prior to inclusion (i.e. discharged ≤1 week prior to inclusion).	Planned revascularisation, TAVI, MitraClip and/or CRT implantation within 3 months after inclusion
Owning a smartphone and able to use an application	Known alcohol or drug abuse
Written informed consent obtained	Terminal renal insufficiency with haemodialysis or peritoneal dialysis
	Impairment or unwillingness to use the digital support equipment (e.g. dementia, impaired self-determination, lacking ability to communicate)
	Existence of any non-cardiac disease reducing life expectancy to less than 1 year
	Age <18 years
	Participation in other treatment studies or remote patient management programmes

Table 1 – Inclusion and exclusion criteria. NYHA: New York Heart Association. LVEF: left ventricular ejection fraction. CRT: cardiac resynchronisation therapy. TAVI: transcatheter aortic valve implantation.

Digital support platform

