At inclusion, an account on the smartphone application will be created for the patient and the application will be installed on the patient's smartphone. Instructions on how to use the application will be provided. Patients will be included for 6 months in which they will be asked to use the different modalities of the smartphone application. There will be low-threshold contact with a study nurse if the patient doesn't use or doesn't know how to use the application, as well as when predefined alarm limits are crossed. In case of patients that are

very motivated to participate in the intervention but do not own a smartphone, a smartphone can be provided by the study sponsor for the duration of the study. No costs will be charged to the patient, also in case of loss or damage

Personalised alarm limits that can be predefined include:

- Heart rate: an upper rate will be set to detect possible atrial fibrillation
- Weight gain: ideal weight and alarm weight can be set by the case nurse.
- Blood pressure: hypotension (under normal limits for the specific patient) and extreme hypertension.
- Not using the application, no measurement input by the patient for a predefined time.

After 6 months the inclusion will be ended. If the patient and the care providers deems it necessary for the continuity of care, they may continue using the application after the 6 months period of the study. A new informed consent document should be signed and the application, inside or outside the study, will remain the same. Only the data collected during the 6-month period of the study will be used for the initial data analysis. Further data analysis of the additional data after 6 months may take place in a second stage. 6 months after the end of the study, during a routine appointment (standard of care) of the patient with his cardiologist, he will be asked to answer questions about his well-being again.

Data collection during the trial

Data that will be collected by the smartphone application and the caregiver application for analysis purposes throughout the trial includes parameter measurement (blood pressure, heart rate, weight), medication adherence by using the medication module, and patient-reported outcome questionnaires. In the caregiver dashboard application information on time spent on the caregiver dashboard application and all input (time spent, change in therapy, contacts) by caregivers (nurses, cardiologists, others) will be collected.

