Interventions because of the trial

Personalised alarm cut-offs can be programmed by the caregiver team. There is no scheduled study contact on top of the usual care contacts. In case of application alarms being triggered, the patient will be called and the situation will be assessed. If needed, the problem will be discussed with a cardiologist. In emergency situations, the patient will be asked to present to the emergency department.

Monitoring of alarms will not be continuous and will only take place during working hours throughout the working week (Monday to Friday) and patients will be instructed to call their general practitioner, the hospital, or the emergency number in case of problems and not to wait until they are contacted.

End-of-trial assessment

At the end of the trial, the assessments listed in Table 2 will be performed. Cost-related data will be collected: healthcare resource use, hospitalisation time, tests, procedures, and health expenditure. Cost-effectiveness will be calculated using healthcare cost data and work productivity and impairment (WPAI) questionnaire to calculate incremental cost-effectiveness ratio (ICER).

Re-evaluation at 12 months

After the end of the inclusion at 6 months, a re-evaluation of outcome parameters will take place at month 12 to evaluate the continued effect of the intervention after cessation.

	Baseline	Final visit month 6
Informed consent and patient information	X	
Medical history: past medical history, symptom control, NYHA classification, smoking behaviour, current medication	X	X
Physical examination including weight, height, blood pressure, heart rate	X	X
Length of initial hospital stay	X	
Registration of medication	X	X
Echocardiography	X	X
12-lead ECG	X	X
Laboratory tests: haemoglobin, haematocrit, leukocytes, thrombocytes, sodium, potassium, creatinine, NT-proBNP	X	X
ePROs: KCCQ-12, EQ5D, HeartQoL, PHQ9, HLS-EU-Q16, EHFSB-9, SUTAQ, WPAI.	X	X
Registration of events: hospitalisation (with the length of stay), emergency department visit, death		X
Cost-evaluation		X

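### The ICER sets cost accumulated over 6 months against a QOL difference not tied to time or survival, so it cannot be read as cost per QALY

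*Protocol*

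**What the plan says.** All places are in the protocol.

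- **Outcome scale.** Health economic analysis: "Costs and outcomes (utilities) will be compared by calculation of the incremental cost-effectiveness ratio (ICER"). The formula that follows divides a cost difference by an effectiveness difference, both against the historical cohort.
- **Numerator.** Same section: "The incremental cost represents the difference in total average cost per patient between the intervention group and the historical cohort or the participation refusals". Besides the direct costs of the intervention, the costs counted are "the care utilisation recorded during the inclusion of the trial". Smartphone intervention gives the length of inclusion: "Patients will be included for 6 months in which they will be asked to use the different modalities of the smartphone application".
- **Denominator.** Health economic analysis: "Effectiveness will be calculated by comparing QOL in the intervention group versus the participation refusals". No instrument, time point, time weighting or handling of deaths is given.
- **Data in participants.** Table 2 lists, at baseline and month 6, "ePROs: KCCQ-12, EQ5D, HeartQoL, PHQ9, HLS-EU-Q16, EHFSB-9, SUTAQ, WPAI", and registers deaths at month 6. Outcomes are re-evaluated at month 12.
- **Data in refusers.** Patient recruitment: "Patients refusing participation will also be asked to complete a quality of life (QOL)-questionnaire at 6 months and 12 months". The questionnaire is not named, no entry value is planned, and no recording of vital status is described.
- **Data in the historical cohort.** Health economic analysis: "Hospital bills and hospital administrative data based on the international classification of disease (ICD)-codes will be collected". No QOL is mentioned.

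End-of-trial assessment and Table 3 name cost data and the WPAI as inputs to cost-effectiveness. EQ5D is not linked to the ICER anywhere, and QALYs are not mentioned.

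**The concern.** The two parts of the ratio are on different time scales. Cost is a total that grows as patients are followed. A QOL or utility difference is a level at a moment. Followed as written, the ratio changes with the length of follow-up even when the effect of the programme does not.

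Survival is also outside the ratio. Only people alive to answer can contribute QOL unless a value is assigned to those who died, and none is. A death can end later costs while leaving measured effectiveness untouched. All-cause mortality is part of the combined clinical endpoint in Table 3, so deaths are expected to matter.

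Demonstrating cost-effectiveness is a stated objective, and the Discussion presents the cost analysis as input to a reimbursement decision. A ratio labelled ICER and described in terms of utilities invites a cost-per-QALY reading that it cannot support.

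**Working it through.** The protocol states no ICER, QALY or threshold value, so there is no figure to reproduce. The check asks how far a ratio per utility point differs from a ratio per QALY for the same data.

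**Inputs.** Horizon 6 months = 0.5 year (Smartphone intervention). Assumed for illustration, not in the protocol: month-6 utility difference D = 0.05 and incremental cost +500 or −500 per patient. The factors below do not depend on these values.

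**Formulas.** Ratio per utility point = C / D. Ratio per QALY = C / A, where A is the area under the between-group utility difference from 0 to 0.5 year. Understatement factor = D / A.

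**The two simplest trajectories, C = +500**

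- As written: 500 / 0.05 = 10,000 per utility point.
- Constant gap: A = 0.5 × 0.05 = 0.025 QALY; 500 / 0.025 = 20,000 per QALY; factor 2.
- Linear growth from zero: A = 0.5 × 0.5 × 0.05 = 0.0125 QALY; 500 / 0.0125 = 40,000 per QALY; factor 4.

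**Other assumed trajectories over 6 months**

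| Shape of the gap | A | Factor |
|---|---|---|
| 2D at entry, falling linearly to D | 0.75D | 1.33 |
| Peak of 2D at month 2, falling to D | 0.667D | 1.5 |
| Rises to D by month 1, then flat | 0.458D | 2.18 |
| Rises to D by month 3, then flat | 0.375D | 2.67 |
| D/2 at entry, rising linearly to D | 0.375D | 2.67 |
| Zero to month 3, then linear to D | 0.125D | 8 |

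So 2 and 4 are not limits. A gap at entry is possible because the refusers are a non-randomised group.

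**Horizon.** Write C = F + cT, where F is one-off cost (devices, staff time for inclusion) and c is incremental running cost per unit of time T. With a constant gap, (F + cT) / D rises with T whenever c is positive, and doubles with T when F is zero. Over 12 months the constant and linear shapes give factors of 1 / 1 = 1 and 2 / 1 = 2, so the conversion is itself tied to the horizon.

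**Deaths.** Assume utilities of 0.75 and 0.70 among the living, constant over time, and deaths spread evenly over 6 months. QALYs per patient = 0.5 × u × (1 − m/2), with m the 6-month mortality. The survivor difference is 0.05 in every case.

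- 10% v 10%: 0.35625 − 0.3325 = 0.02375; factor 2.11.
- 8% v 12%: 0.360 − 0.329 = 0.031; factor 1.61.
- 12% v 8%: 0.3525 − 0.336 = 0.0165; factor 3.03.

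The survivor comparison cannot tell these three cases apart.

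**Cost saving, C = −500.** −500 / 0.05 = −10,000 per utility point, against −20,000 or −40,000 per QALY. Lower cost with better QOL is dominance on either scale.

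**The case against.** The strongest objection is that the protocol never promises a cost per QALY and sets no threshold. A cost per utility point is hard to interpret but is not false arithmetic, and turning EQ5D values into time-weighted outcomes is often left to an analysis plan, which is not shown here. That stands in part: silence on QALYs alone would be no finding. But this section does more than stay silent. It writes out a formula and says how effectiveness is obtained. Moreover, an analysis plan cannot supply data that are not collected: refusers have no entry value, no named instrument and no described vital status.

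A reader might infer that the trial will report an ICER 2 to 4 times too favourable. The documents do not support that. They do not say the ratio will be read as cost per QALY. The factors come from two assumed trajectories, and others give about 1.3 to 8. The direction requires a positive incremental cost as well as a positive utility gain, whereas the protocol plans to calculate a cost reduction. Nor does it follow that every death lowers cost: a death after an unplanned admission may raise it. Doubling follow-up also need not double cost, because part of it is one-off.

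**Conclusion.** The point holds as a mismatch of definition: accumulated cost over an outcome with no time and no survival in it. As defined, the ratio depends on the horizon, does not register deaths as lost benefit and cannot be set against a cost-per-QALY benchmark.

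The size is conditional. If incremental cost and utility gain are both positive and the ratio is read as cost per QALY over 6 months, it understates that figure by a factor of 2 (constant gap) or 4 (linear growth from zero), before any difference in mortality. Both are scenarios. With savings and better QOL, the conclusion of dominance is unaffected.

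A firmer inconsistency sits in the same section. The formula takes effectiveness from the historical cohort, for which only billing and administrative data are planned, while the text takes it from the refusers.

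**What to change.** In Health economic analysis:

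1. Define effectiveness as QALYs over the same 6 months as costs: the area under the EQ5D utility curve, with utility 0 from the date of death.
2. Name EQ5D in the refusers' questionnaire, and record an entry EQ5D value and vital status, with date of death, for them.
3. Where the entry value is missing, report the QALY difference under labelled trajectory scenarios, for example constant gap (D × 0.5 year) and linear growth from zero (D × 0.25 year). Do not call these bounds.
4. Use one comparator in both parts of the ratio. On the planned data only the refusers can supply effectiveness, and the section already plans to collect their costs. The cost comparison with the historical cohort can then be reported separately, not as an ICER.

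Participants already supply EQ5D at baseline and month 6, and their deaths are registered, so nothing new is needed from them. The cost is one short extra questionnaire and vital status for refusers, some protocol wording, and an ICER that may look less favourable. Without the entry value and vital status, the refusers' QALYs would rest on assumption.
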